Treatment with the PCSK9 inhibitor, evolocumab has been shown by intravascular ultrasound to be associated with a reduction of percent atheroma volume after 1.5 years of treatment; however, it is not known how evolocumab affects specific coronary plaque types and plaque inflammation [6, 7]. Although intravascular ultrasound (IVUS) can provide quantitative measurements of total atheroma volume, it is an invasive technique with associated procedural risks and therefore not practical for routine clinical monitoring of response to medical therapy. Quantitative assessment of changes in plaque burden, plaque composition and vascular inflammation in response to treatment with a PCSK9 inhibitor with noninvasive imaging (CCTA and positron emission tomography (PET) can provide a comprehensive assessment of pathophysiologic changes before and during treatment.

Our group has developed and extensively validated a semiautomatic method of comprehensive measurements of coronary plaque burden and plaque composition in the entire coronary artery tree on CCTA (Autoplaque) [8-12]. Among the many Autoplaque measurements are noncalcified plaque volume, low density non calcified plaque volume, the latter representing the necrotic core. We have shown strong correlation of noncalcified plaque volume with IVUS [10] and have documented excellent reproducibility of the various plaque measurements [12]. In 116 patients having serial studies over 3.5 ± 1.6 years, we have preliminary evidence that a 10% reduction in LDL is associated with an interval reduction in the volumes of all components of non-calcified plaque including adverse plaque characteristics associated with plaque instability and predictive of future cardiac events [13, 14].

With PET, our co-investigators have shown that microcalcification activity within coronary arteries and the aorta-reflecting the rate of deposition of calcium-can be assessed by 18F sodium fluoride

(NaF) PET. This process is considered to be governed by the degree of plaque inflammation, and as such another marker of plaque vulnerability [15]. Thus, 18F NaF PET allows the assessment of the effect of therapy on a measurement related to plaque inflammation.

STUDY DESIGN

This is an early development, single-arm, prospective, open-label study of evolocumab injection in patients with calcified plaque in the coronary artery detected by CCTA. Fifty-five (55) evaluable subjects will be enrolled in the study.

OBJECTIVES

1. To test the hypothesis that PCSK9 (proprotein convertase subtilisin kexin type 9) inhibitor, evolocumab, reduces the volume of noncalcified plaque in coronary arteries as measured by coronary computed tomography angiography (CCTA)
2. To determine the components of non-calcified coronary artery plaque that are affected by treatment with evolocumab.
3. To determine if lipid lowering with evolocumab is associated with changes in microcalcification in atherosclerotic plaque as measured by F18-NaF PET

SPECIFIC AIM

To quantify changes in coronary plaque volumes and plaque composition in patients treated with evolocumab.

Hypothesis: Patients treated with evolocumab demonstrate a reduction of coronary non-calcified plaque volume, including a preferential reduction in volume of low density non-calcified plaque components

EXPLORATORY AIMS

To evaluate whether patients treated with evolocumab demonstrate reduced microcalcification activity in the coronary arteries as assessed by 18F NaF.

Hypothesis: Treatment with evolocumab will be associated with reduced rate of coronary plaque inflammation which may be detected as a reduction in the rate of microcalcification activity.

SUBJECT DESCRIPTION

Treatment Group

Inclusion Criteria

Treatment group will be comprised of 55 adult male and female patients who satisfy the following enrollment criteria:

- Evidence by CCTA of noncalcified coronary artery plaque ($>440 \text{ mm}^3$)
- On-label indications for evolocumab treatment which includes the following criteria:
Those who have established cardiovascular disease defined as acute coronary syndrome, history of myocardial infarction, stable angina or unstable angina, coronary or other arterial revascularization, stroke, transient ischemic attack, or peripheral arterial disease presumed to be of atherosclerotic origin.
- Non-calcified plaque (NCP) volume of 250 mm^3 or more in any single plaque in patients who do not have a total NCP $>440 \text{ mm}^3$

Exclusion Criteria

- Creatinine $> 1.5 \text{ mg/dL}$ prior to imaging
- History of allergy to iodine contrast agents
- Allergy to evolocumab or any other ingredients contained in study drug, including latex
- Pregnancy
- Women who are breastfeeding
- Active atrial fibrillation
- History of coronary artery bypass graft
- Inability to lie flat
- Inability or unwilling to give informed consent
- Major illness or life expectancy $<1 \text{ year}$
- Planned coronary revascularization or major non-cardiac surgery in the next 12 months
- Previously or currently on evolocumab
- Specific to beta-blocker administration: hypersensitivity or allergy to metoprolol or other beta-blockers, SBP $<100 \text{ mmHg}$, serious heart problems, such as cardiac failure (hypertension and angina), congestive heart failure, heart block, severe sick sinus syndrome, circulation problems, asthma or other breathing problems, peripheral artery circulatory disorders.

Recruitment and Enrollment

Treatment group

Investigators and/or the study coordinator will perform a weekly review of patients who have had a coronary calcium screening in the past month with coronary artery calcium (CAC), patients who have had a coronary CT angiogram with atherosclerotic plaque, and those who have plaque as documented during invasive angiography in the catheterization lab at Cedars-Sinai Medical Center.

Among these patients, those who meet the inclusion criteria will be recruited to participate. Any information available in the patient's Cedars-Sinai medical records that can help determine eligibility will be viewed. The patient's cardiologist or other medical provider who ordered the CCTA or the invasive angiogram will be approached regarding appropriateness of recruiting the patient. The patient will then be contacted by an investigator or study coordinator for potential consent and participation."

All potential participants will be given enough time to consider the study. It will be explained that their participation is voluntary and will not affect their clinical care should they agree to participate or decline. We will provide a copy of the consent form to patients prior to the day of the study.

The subject's clinical status will be monitored for any adverse change prior to signing informed consent as well as prior to beginning any research procedures.

Feasibility: As of October 2017, we identified from our database 160 patients who have undergone sequential CCTA in whom total cholesterol and LDL values are also known, and who met indications for evolocumab.

DESCRIPTION OF PROCEDURES (Treatment Group)

The study protocol is comprised of a first CCTA (obtained clinically within 90 days prior to enrollment or at the first imaging visit for research purposes) and 18F-NaF PET, treatment with evolocumab for 18 months and a follow up CCTA and 18F-NaF PET.

All subjects will receive blood sampling and 18F-NaF PET scan during their initial visit. Subjects can expect to be at CSMC for approximately 5 hours.

Following the 18F-NaF PET scan, the first injection of evolocumab will be administered by a nurse at CSMC. Patients will be given instructions on how to prepare and administer evolocumab prior to use and will be provided a 6 months' supply of evolocumab for self-administration at each onsite visit.

In patients without homozygous familial hypercholesterolemia (FH), evolocumab will be self-injected as follows: 140mg every 2 weeks or 420mg once a month subcutaneously.

Patients with homozygous FH will be instructed to administer 420mg subcutaneously once a month by giving 3 injections consecutively within 30 minutes using the single-use prefilled autoinjector.

Patients will undergo monitoring for adverse effects and for adherence with treatment every 3 months (phone calls at 1,3, 9, and 15 months of treatment and on-site visit with a nurse practitioner (NP) or MD at 6, 12 and 18 months of treatment. Patients will also receive a sharps container to safely discard all used syringes immediately after administration of the dose. The filled container will be returned during each on-site follow-up visits for drug accountability and proper disposal. After 18 months of treatment with evolocumab, patients will undergo a CCTA and 18F-NaF PETCT. Acquisition protocols will be identical to their baseline study.

Blood testing (estimated procedure time = 15 minutes)

Prior to beginning any imaging, patients will have blood drawn from a peripheral vein (<30 cc) to check creatinine (I-STAT® (Abbott Laboratories). Plasma and serum samples will be drawn for assessment of plasma and serum biomarkers including inflammatory, cardiac, and lipid markers, which may include C-reactive protein, IgM, interleukin-12 p70, tumor necrosis factor α , erythrocyte sedimentation rate, lipoprotein-associated phospholipase (Lp-PLA2), brain natriuretic peptide, oxidized low-density lipoprotein (LDL), high-sensitivity troponin as well as novel biomarkers being developed in the laboratory of co-investigator [name] [name], PhD.

18F-NaF PET Scan (estimated procedure time = 4 hours from time of 18F NaF injection)

- 1) Study subjects will be administered a dose of 250 MBq 18F-NaF intravenously.
- 2) All subjects will undergo dual cardiac and respiratory-gated PET-CT imaging of the thoracic aorta with a GE Discovery PET/CT 710 (GE Medical Systems) 180 minutes after injection. Scanning will utilize an attenuation correction CT scan (non-enhanced 120 kV and 50 mA), followed by PET imaging of the thorax in list-mode for 30 minutes.

CCTA (estimated procedure time = 0.5 hours)

The protocol used is the standard clinical protocol for CCTA that was employed in the baseline CCTA. The typical protocol is as follows:

- 1) CCTA will be performed using a SOMATOM Definition scanner (Force, Siemens Medical) as previously described [16]. When needed, oral and/or intravenous beta blockers (metoprolol) is administered to achieve a target heart \leq 70 beats/min (bpm). Immediately before CTA scanning, 0.4 or 0.8 mg of sublingual nitroglycerin (ScielePharma, Alpharetta, Georgia) is administered. Images are acquired after a bolus injection of 80-100 ml contrast (Omnipaque or Visipaque, GE Healthcare, Princeton, New Jersey) at a rate of 5-6 ml/s, using either axial or helical scanning with dose modulation. Scanning parameters will include: tube voltage of 120 or 100 kVp, tube current 600 to 800 mA, depending on patient size; table feed/scan 3.8 mm; and pitch factor 0.2-0.4 (Heart rate dependent). Real-time bolus-tracking technique is used to trigger scan initiation. Axial images will be reconstructed at 0.6-mm slice thickness, 0.3-mm slice increment, 250-mm field-of-view, and 512 \times 512 matrix.

Follow-up calls and visits

Phone Calls: At the beginning of the 3rd, 9th, and 15th month of treatment with evolocumab, patients will be contacted by phone to determine if they have had any adverse effects from evolocumab and to assess their adherence to monthly injections. A final phone call will also be made 3-7 days after the last dose and scan to determine adverse events and concomitant medications.

Visits to Cedars-Sinai: At the beginning of the 6th, and 12th months of treatment with evolocumab, patients will be seen by a NP at Cedars Sinai for on-site follow-up safety visits. Adherence to treatment and adverse effects will be assessed at these visits. Blood will be drawn at these visits to measure serum total cholesterol, LDL, HDL and TG as well as to confirm that patient is not pregnant. Patient will return the sharps container with the used syringes to CSMC research staff and new container will be dispensed. An additional 6 months' supply of evolocumab will also be dispensed at the follow-up visits (months 6 and 12), and re-training of injection technique/disposal will be provided as needed.

There will also be a final visit at the end of 18 months of treatment at which time adverse events and adherence will also be assessed and blood will be collected for a lipid panel and to confirm pregnancy status; samples will be stored for biomarker assessment. Patients will undergo a CCTA and PET-CT at that time as described above.

Patients who discontinue the study after 12 months of treatment with evolocumab will be encouraged to undergo CCTA and 18F-NaF PET, which will be the EOS (end-of-study) imaging for this group.

Study Schedule

Study Schedule: Effect of PCSK9 inhibitor, Repatha on coronary artery plaque composition and microcalcification by Coronary CTA and F18-NaF PET

Study Procedure	Visit 1	Visit 2	Visit 3	Visit 4	Visit 5	Visit 6	Visit 7	Visit 8	Visit 9
	Screening/ Enrollment	F/U Call	F/U Call	Safety F/U	F/U Call	Safety F/U	F/U Call	Final On-site Visit	EOS ^h
Initial visit (1 or 2 days)	1 month ± 7 days	3 months ± 30 days	6 months ± 30 days	9 months ± 30 days	12 months ± 30 days	15 months ± 30 days	18 months ± 30 days	3-7 days after Visit 8 ± 30 days	
Informed consent	x			x		x		x	
Eligibility Criteria	x								
Demographics	x								
Medical History	x								
Concomitant medication	x	x	x	x	x	x	x	x	x
Adverse Events	x	x	x	x	x	x	x	x	x
Labs	x			x		x		x	
Pregnancy Test ^a	x			x		x		x	
CCTA ^b	x ^b							x	
18F-NaF PET	x							x	
Administer IP ^c	x			x		x		x	
IP site monitoring	x			x		x		x	
IP re/training ^d	x			x		x			
Monitor drug adherence	x	x	x	x	x	x	x	x	
Dispense IP ^e	x			x		x			
Dispense sharps container ^f	x			x		x			
Provide drug diary ^g	x			x		x			
Collect drug diary				x		x		x	
Return IP ^h				x		x		x	

^a If female subject is of child bearing age, and the first day of their last menstrual cycle is not within the past 30 days, a one-step HCG urine test will be done

^b Patients who have already undergone a CCTA as part of screening within the past 90 days, will not need to undergo a CCTA at the time of their initial 18F-NaF PET scan

^c IP will be administered subcutaneously by a nurse and then self- administered for the rest of the study. At Visits 4, 6, and 8 subject will administer the IP in the presence of a medical professional to ensure proper technique/compliance

^d Nurse will train subject at Visit 1. At Visits 4, 6, and 8 subject will administer IP in the presence of medical professional and re-training will be provided as needed.

^e Six months supply of IP will be dispensed to subject at Visits 1, 4, and 6

^f New sharps container will be provided for subject to discard used IP autoinjectors

^g Subject will discard autoinjector after each administration of IP in provided sharps container, and return the filled container to the next on-site visit (safety f/u)

^h End of Study (EOS) safety phone call will be made 3-7 days after dose and scan (± 30 days)

ⁱ Subject will be provided a drug diary to document date, time, and location of each self-administration and return the completed diary to the next on-site visit (safety f/u)

COLLECTION OF CLINICAL INFORMATION

Clinical information including age, sex, BMI, ASCVD risk factors, medications and dose of statin and antiplatelet therapy and laboratory data will be collected.

DATA PROCESSING AND ANALYSIS

I. Data anonymization/blinding

a. Anonymization

- i. DICOM files of each CCTA and PET for each subject who completed the follow-up scan were anonymized of all identifiers except for the Series Description, using “dicononymize”. A randomization generator randomized all baseline and follow-up scans and provided new subject IDs (prefix “EVO”) and procedure IDs (prefix CT or PET, depending on the procedure).
- ii. CTs and PETs related to the same visit have the same 4 alpha-numeric ID with the CT or PET prefix to signify which studies were evaluated together. A linking file was accessible only to the study manager who were unblinded to which scans are baseline and follow-up.
- iii. Once all scans are anonymized, the folder was zipped and uploaded to a BOX folder, accessible to the PIs and readers.

b. Blinding

- i. In order to blind readers to the order of the scans, a linking file was created to randomize the subject’s ID, order of enrolment and order of scan

II. CCTA image analysis

- i. The CCTA imaging core lab (Cedars-Sinai Medical Center, Los Angeles, CA, USA) performed qualitative and quantitative measurements of CCTA using AI enabled plaque quantification research software (Autoplaque, Cedars-Sinai Medical Center, Los Angeles, CA, USA). All qualitative and quantitative analyses were reported as per-patient and per-lesion level.
- ii. All coronary segments ≥ 2 mm according to the 18-segment SCCT model were evaluated by level III-experienced readers blinded to clinical and PET data. Two serial scans (date blinded) were assessed at the same time. Overall study quality was recorded using a 5-point image quality assessment tool (excellent/good/fair/poor/non-diagnostic). The presence of coronary

plaque was defined as any tissue structure $<1\text{mm}^2$ that existed either within the coronary artery lumen or adjacent to the coronary artery lumen that could be discriminated from surrounding pericoronary tissue or the vessel lumen itself. Between two serial scans, lesions were matched between two serial CCTAs using lesion location (involved coronary segment) and branch points as landmarks.

iii. Qualitative APC measurements

1. Stenosis severity was visually graded according to the CAD-RADS (Coronary Artery Disease – Reporting and Data System). All plaques were qualitatively assessed for the presence of adverse plaque characteristics: positive remodeling, low attenuation plaque, spotty calcification, and napkin-ring sign. Positive remodeling was defined by a vessel remodeling index >1.1 . Low attenuation plaque was defined by the presence of any voxel <30 Hounsfield units (HU). Spotty calcification was defined as visually detectable calcification <3 mm in any direction within a plaque. Napkin-ring sign was defined as noncalcified plaque with a central area of hypoattenuation surrounded by a peripheral rim of hyperattenuation. High risk plaque was defined as presence of two or more APCs.

iv. Quantitative measurements

1. In axial and multiplanar views, the expert level III reader placed a region of interest in the ascending aorta to define normal blood pool and control points in the coronary lumen to define the centerline. The proximal and distal limits of lesions was manually defined, following which adaptive scan-specific Hounsfield Unit (HU) thresholds for plaque components were automatically generated. Automatic segmentation of the vessel wall and lumen were performed with manual adjustment as required. Plaque volume (mm^3) was calculated on a per-lesion level for the following components: total plaque, calcified plaque, noncalcified plaque, and low-attenuation plaque (defined by a fixed attenuation threshold <30 HU). Quantitative diameter stenosis (%) was calculated as the ratio of minimal lumen

diameter to the mean of 2 (proximal and distal) non-diseased reference points. The contrast density difference is defined as the maximum percent difference in contrast density (the luminal attenuation per unit area over 1-mm cross-sections) within the plaque, with respect to the proximal normal reference cross-section.

III. PET image analysis

i. PET reconstruction

1. PET images were reconstructed into 4 cardiac phases using a vendor provided software (JS-Recon12, Siemens, Knoxville, TN, USA). All PET image reconstructions were performed with corrections for time-of-flight and point-spread function. Using 4 cardiac gates, we reconstructed the data on a 256×256 matrix (109 slices, slice thickness 2.027 mm) using 2 iterations, 21 subsets and 5-mm Gaussian filter.

ii. Cardiac Motion correction

1. Cardiac motion corrected images were obtained from the gated PET reconstructions through PET-PET image co-registration using a diffeomorphic registration and dedicated software (FusionQuant version 1.19.2.7, Cedars-Sinai Medical center).

iii. Image registration

1. Prior to image analysis, the PET reconstructions were registered to the CCTA images, using a rigid translation of the PET images. The PET to CCTA registration was ensured using five key points of reference; sternum, vertebrae, blood pool in the left and right ventricle (based upon high ^{18}F -NaF activity in the blood pool in comparison to the surrounding myocardium), and the great vessels.

iv. Blood clearance correction

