Hypersensitivity reactions (e.g., rash, urticaria) have been reported in patients treated with evolocumab, including some that led to discontinuation of therapy. If signs or symptoms of serious allergic reactions occur, discontinue treatment with evolocumab, treat according to the standard of care, and monitor until signs and symptoms resolve. Please see section 6 of the appendix [Repatha prescribing information.pdf](#).

PRIMARY ENDPOINT

1. Change in noncalcified coronary artery plaque volume from baseline to month 18 of treatment with Evolocumab.
2. Change in plaque composition (low density non-calcified and calcified) from baseline to month 18 of treatment with Evolocumab.

STATISTICAL ANALYSIS PLAN

For all statistical analyses, two-sided tests will be conducted and p-values < 0.05 will be considered significant. Continuous variables will be presented as mean \pm standard deviation (SD) or median (interquartile range) as appropriate. Annualized rate of change in total plaque volume, and the volume of non-calcified plaque, specifically, low density non calcified plaque components will be analyzed. Mean values will be compared using a paired Student's t-test median values will be compared using the Wilcoxon rank-sum (Mann-Whitney) test. The relationship between decrease in LDL and changes in plaque volume and individual plaque components per year will be evaluated after adjusting for the effects of confounding variables including age, diabetes, hypertension, smoking, family history of premature coronary artery disease, statin use, baseline LDL and baseline plaque volume. Reproducibility of measurements of, volume of plaque components and total plaque volume will be assessed using intra-class correlations and coefficients of variation.

SAMPLE SIZE POWER CALCULATIONS

In a study of 116 patients who underwent sequential CTA, we observed a reduction in total plaque volume and NCPV among patients who experienced a reduction in LDL of >10% of their baseline LDL level under the influence of statins alone. Based on this preliminary work, we expect to detect a difference of at least 50mm³/year in non-calcified plaque volume (Δ NCPV = NCPV_{pre-treatment} – NCPV_{post-treatment}) among patients who were treated with evolocumab. From our data, we estimate the population standard deviation for measurement of (Δ NCPV/year) to be 115mm³. Using a paired t-test with a power of 80% and an alpha value of 0.05, we would need 44 patients in our treatment group.

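### The planned analyses of component volumes cannot tell a preferential fall in low-density noncalcified plaque from a proportional one

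*Combined protocol and SAP*

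**What the plan says.** **Hypothesis (Specific Aim).** Treated patients are expected to show a fall in NCP volume, "including a preferential reduction in volume of low density non-calcified plaque components". This sits under the protocol's one Specific Aim. The exploratory aim concerns 18F-NaF uptake.

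**Objective 2 (Objectives).** "To determine the components of non-calcified coronary artery plaque that are affected by treatment with evolocumab". It asks which components change and does not rank them.

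**Second item under Primary Endpoint.** "Change in plaque composition (low density non-calcified and calcified) from baseline to month 18 of treatment with Evolocumab".

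**Statistical Analysis Plan.** The analysis variables are given as: "Annualized rate of change in total plaque volume, and the volume of non-calcified plaque, specifically, low density non calcified plaque components will be analyzed". The tests are given as: "Mean values will be compared using a paired Student's t-test median values will be compared using the Wilcoxon rank-sum (Mann-Whitney) test". A regression follows: "The relationship between decrease in LDL and changes in plaque volume and individual plaque components per year will be evaluated after adjusting" for a list of covariates.

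**Measurement (Data Processing and Analysis, CCTA image analysis, Quantitative measurements).** Plaque volume in mm³ is "calculated on a per-lesion level for the following components: total plaque, calcified plaque, noncalcified plaque, and low-attenuation plaque". The same part of the protocol says that results are reported per patient as well as per lesion. No share or ratio of components is defined.

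**Sample Size Power Calculations.** The 44 patients are derived from the annualized change in total NCP volume only.

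**The concern.** A preferential reduction means that low-density NCP shrinks proportionally more than the remaining NCP. A test of that claim has to set one component against the other within the same patient. The listed analyses each concern a single volume, or the relation of a single volume's change to LDL.

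Low-density NCP is part of NCP, so a uniform shrinkage of all NCP also lowers low-density volume. Uniform shrinkage is a realistic alternative here: the protocol's introduction cites the group's own serial-CCTA data, in which LDL lowering went with falls in every component of NCP.

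At stake is a stated hypothesis with no valid test. A significant fall in low-density volume could be reported as preferential without support, and a real preference could go undemonstrated although the data to show it are in hand.

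**Working it through.** **1. The plan's own figure.** Inputs from Sample Size Power Calculations: difference 50 mm³/year, SD 115 mm³, power 80%, alpha 0.05; two-sided testing from the SAP.

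- Standardized effect: 50/115 = 0.435.
- Normal approximation: (1.960 + 0.842)²/0.435² = 41.5, so 42.
- Paired t-test with the noncentral t distribution: 43 patients give 79.5% power and 44 give 80.5%, so N = 44. The figure reproduces, and 55 − 10 = 45 covers it.

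This N is right for total NCP. It does not address a between-component question.

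**2. What separates the two hypotheses.** Let low-density volume L fall by a proportion *a* and remaining NCP volume R by a proportion *b*. The low-density fraction moves from L/(L + R) to L(1 − a)/[L(1 − a) + R(1 − b)], which is smaller exactly when a > b. The plan's difference over 18 months is 50 × 1.5 = 75 mm³. On an assumed baseline of 600 mm³ that is 12.5%. With an assumed low-density share of 8% (48 and 552 mm³):

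| Case | Low-density | Remaining | Total NCP | Fraction |
|---|---|---|---|---|
| Proportional: both −12.5% | 48 → 42 | 552 → 483 | 600 → 525 | 8.0% → 8.0% |
| Preferential: −25% and −12.5% | 48 → 36 | 552 → 483 | 600 → 519 | 8.0% → 6.9% |

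In both rows every volume falls from baseline. Only the fraction distinguishes them. The absolute changes do not help: low-density NCP loses fewer mm³ than the remainder (12 against 69) even when its loss is preferential.

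**3. Separate tests when there is no preference.** Assume that the percent changes in low-density and remaining NCP have equal SD, that both have the standardized effect 0.435, and that their within-patient correlation is ρ. With 44 patients and 20,000 simulated trials per value of ρ:

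| ρ | Low-density fall significant | Low-density significant, remaining NCP not | Direct paired contrast significant |
|---|---|---|---|
| 0.3 | 81% | 13% | 5% |
| 0.5 | 81% | 11% | 5% |
| 0.7 | 80% | 8% | 5% |
| 0.9 | 81% | 5% | 5% |

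The second column is power for a fall that is real. The third is the pattern most likely to be misread as preference. The last column shows that a direct contrast holds its nominal level.

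**4. Power of a direct contrast.** The documents give no effect, SD or correlation for one, so no single N follows. Under the same assumptions, but with the low-density effect *k* times that of the remaining NCP, the standardized effect of the difference in percent changes is (k − 1) × 0.435/√[2(1 − ρ)]. For k = 1.5 and ρ = 0.3 this is 0.217/1.183 = 0.184. Power at N = 44, with the N for 80% power in brackets:

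| k | ρ = 0.3 | ρ = 0.5 | ρ = 0.7 | ρ = 0.9 |
|---|---|---|---|---|
| 1.25 | 9% (932) | 11% (667) | 15% (401) | 35% (135) |
| 1.5 | 22% (235) | 29% (169) | 44% (102) | 88% (36) |
| 2 | 66% (61) | 80% (44) | 95% (27) | >99% (11) |

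The difference in percent changes stands in for the fraction here. The two address the same question, but their power will not be identical.

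**The case against.** **The pairing is not spelled out.** The SAP does not say what the paired t-test pairs, so the statement that each component is tested against its own baseline is an inference. This stands. It is the natural reading, because the endpoints are changes from baseline and the NCP change is defined as pre- minus post-treatment. No pairing across components is stated anywhere.

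**Composition could mean share.** The Specific Aim names plaque volumes and plaque composition separately. If the second endpoint meant a share, a paired test of it would be close to the fix proposed below. The reading is possible, but the measurement section and the SAP define and analyze volumes only, so a defining sentence is needed either way.

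**The claim is a small part of the plan.** A reader might infer that half of the hypothesis cannot be answered. The documents do not support that. Preferential appears once, in a subordinate clause; Objective 2, on which components are affected, is served by component-wise tests; and the sample size concerns total NCP.

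**Two significant falls are not an error.** Two simulations of a uniform 12.5% fall (600 mm³, 8% share, three assumed noise levels) found both total and low-density NCP significant in 50% to 72% and in 44% to 67% of trials. A reader might take these as false-positive rates for preference. They are power to detect two true falls, and the SAP contains no rule that turns two significant tests into a preferential claim. Under similar assumptions, the pattern of low-density significant and total NCP not occurred in about 3% of trials.

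**The fraction has its own difficulties.** Low-attenuation plaque uses a fixed cut-off of 30 HU, while other component thresholds adapt to the scan, so the ratio may mix two systems. Power may also be low. Both stand as caveats. Neither gives the existing tests any bearing on preference.

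**Conclusion.** The point holds. No analysis in the plan compares low-density NCP with the rest of the NCP, so a proportional fall and a preferential one cannot be told apart. The total-NCP analysis and N = 44 are unaffected.

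The logical gap does not depend on any assumed number. Its size does. If the low-density component shares the plan's standardized effect of 0.435, its own test is significant in about 80% of trials without any preference. The more misleading pattern of one component significant and the other not arises in roughly 5% to 13% under equal standardized effects, and in about 3% when total NCP is the comparator under the assumed volumes and noise. None of these is a false-positive rate of a rule in the SAP. They show how little the separate tests say about preference.

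Power for a direct contrast at N = 44 is not established: about 22% to over 99% for k between 1.5 and 2, and lower for a weaker preference.

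**What to change.** Prespecify one within-patient contrast in the SAP:

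- **Variable.** Per patient and scan, low-density NCP volume summed over lesions, divided by total NCP volume summed over the same lesions. State that the low-density component is the one below 30 HU and that the denominator includes it.
- **Analysis.** Paired change from baseline to follow-up with a 95% CI. Write it as follow-up minus baseline, since the sample-size section defines the NCP change the other way round.
- **Scale.** Use the fraction and not a log-ratio. The fraction stays defined when low-density volume is zero, and the entry criteria on NCP volume keep its baseline denominator above zero.
- **Claim.** Call the reduction preferential only if the CI lies wholly below zero. Otherwise report component changes descriptively. Show the low-density volume change beside it, because the fraction also falls if the remaining NCP grows.
- **Position.** Secondary to the total-NCP test, with a statement that N = 44 was sized for total NCP only and that power for this contrast is not established.

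The cost is a few SAP sentences and no new scans, patients or measurements: a cheap improvement. The downside is one extra secondary test that may be underpowered, and a narrower claim if it is not met. If the sponsor does not want the contrast, the word preferential should be removed from the hypothesis or labelled descriptive.
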